Eligibility: age ≥ 18 years; smoked ≥ 5 cigarettes a day for the past year; want to quit smoking within the next 30 days; if concurrently using any other tobacco products (e.g., e-cigarettes), wants to quit using them within the next 30 days; interested in learning skills to quit smoking; willing to be randomly assigned to either condition; resides in the United States; has daily access to their own iPhone or Android smartphone; knows how to download smartphone applications; willing and able to read in English; never used QuitGuide and not currently using other cessation treatment; never participated in our prior studies; no household members already enrolled; willing to complete outcome surveys, and provided contact information for themselves and two relatives. Participants not eligible for or interested in enrolling will be given the smokefree.gov website and the [name] phone number to reach their state's quitline.

Recruitment. We will use a recruitment process modeled after our the smartphone-delivered ACT pilot [21] as well as our web-delivered ACT pilot trial [20]. The study team will design our participant recruitment website which will provide basic information about the study, a FAQ, a brief video describing the study, information about the study team and Fred Hutch, and a portal to the informed consent form, screening, and baseline surveys. The team will also work with the Fred Hutch communications department to design of a series of press releases and Facebook advertisements to be distributed over the course of the recruitment period.

We have extensive experience in designing recruitment materials for increasing racial/ethnic minority enrollment. Specifically, we will further adapt our approach to recruit at least 30% minority and 30% men: (1) the study team will design and distribute several culturally-relevant press releases; (2) develop effective strategies for using the media and the Internet to target minority smokers, including reaching out to minority-specific media newswire services and including on our ads and enrollment website photos from target minority groups; (3), Partner with Fred Hutch's Diversity Council staff design and disseminate minority-specific recruitment materials that will be disseminated to minority media (e.g., PR Newswire Multicultural Markets Newswire); (4) enrollment will be limited to no more than 70% White participants and no more than 70% women, to ensure racial/ethnic minority and male representation.

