Primary assessments. Aim 1: Tobacco outcomes. Primary endpoint: 30-day point prevalence abstinence at 12-months post randomization, as readily comparable to other smoking cessation trials [60] and our ongoing web-based ACT intervention trial (R01CA166646). A 12-month main endpoint accounts for the relapse rates observed between 2 and 12 month follow-up [60, 76, 77]. Moreover, a 12-month endpoint directly addresses the overall need for technology-delivered cessation trials to show longer term benefit (e.g., 12 months) [9-15]. Secondary endpoints: prolonged abstinence (i.e., no smoking since three months after randomization, as consistent with ACT's approach of allowing participants a grace period of several lapses as opportunities to practice ACT skills) and 7-day point prevalence [78]. All endpoints will also be examined at 3 and 6 months post randomization. The secondary definition of cessation will include abstinence from cigarettes **and** these non-cigarette nicotine/tobacco products: e-cigarettes, snus, chewing and smokeless tobacco, hookahs, cigars, cigarillos, tobacco

pipes, and kreteks (clove/tobacco cigarettes). Use of nicotine and tobacco products will be measured at baseline and all follow-up endpoints. We considered continuous monitoring of tobacco but elected not to because (1) it lowers response rates—a confound [30], and (2) effect sizes are similar to point prevalence [31].

We also considered biochemical validation but self-reported smoking is a standard method for assessing technology-based interventions. Evidence suggests false reporting is minimal for low-intensity interventions with no face-to-face contact [79, 80]. Due to cost and low demand characteristics for false reporting, the SRNT Subcommittee on Biochemical Verification recommends biochemical confirmation has low response rates [69] and is unnecessary in population-based studies with limited face-to-face contact and studies where the optimal data collection methods are through the mail or telephone [81].

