Analyses. Aim 1. Our primary outcome hypothesis is that iCanQuit will have significantly higher 30-day point prevalence abstinence at 12 months post-randomization than QuitGuide. **Analyses:** For each comparison of the arms on the primary and all secondary endpoints, we will use a logistic regression model with complete case smoking cessation outcome [9-14]. The model will adjust for all stratification factors as well as baseline factors that might be imbalanced after randomization. In addition, we will conduct these analyses: (1) multiple imputation of missing outcomes [90-92], (2) missing equals smoking outcomes [9-14], (3) using a secondary cessation outcome of no use of cigarettes **and** other nicotine or tobacco products except FDA-approved nicotine replacement therapies. Finally, we will compare the two arms on utilization of their assigned app.

Aim 2. We hypothesize that the iCanQuit arm's (but not the QuitGuide arm's) smoking cessation outcomes will be strongly mediated by these psychological measures that are central to the theoretical model underlying ACT: commitment to quitting and acceptance of internal (a) sensations, (b) emotions, and (c) thoughts that cue smoking. This hypothesis is consistent the ACT model and prior ACT for smoking cessation intervention studies [16, 17, 20, 82]. **Analyses:** For each mediator, the model is expressed as three regression equations that relate the main independent variable X

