Aim 3. We hypothesize that iCanQuit will be more cost-effective than QuitGuide, as measured by cost per quitter, incremental cost-effectiveness ratio (ICER), and incremental cost per quality-adjusted life year (QALY). We will use current good practices of estimating cost-effectiveness, which were articulated by [96], as applied to smoking cessation interventions [77, 97]. First, to examine whether iCanQuit costs less than QuitGuide to help a person quit, we will estimate the incremental cost-per-quitter: difference in total cost of delivering the two interventions [98] divided by the difference in the number of 30-day abstinent participants at 12-months ($\text{Total Cost}_{\text{iCanQuit}} - \text{Total Cost}_{\text{QuitGuide}} / \# \text{Abstinent}_{\text{iCanQuit}} - \# \text{Abstinent}_{\text{QuitGuide}}$). Total delivery cost assessments are described in Section 3.3.11. Second, to estimate whether iCanQuit costs less than QuitGuide per life year added [77], we will calculate standard Incremental Cost-Effectiveness Ratios (ICER): $\text{Total Cost}_{\text{iCanQuit}} - \text{Total Cost}_{\text{QuitGuide}} / \# \text{Life Years Added}_{\text{iCanQuit}} - \# \text{Life Years Added}_{\text{QuitGuide}}$. Life years added attributable to each intervention's 12-month primary endpoint effect size will be derived from the life years estimates, reported in Stapleton & West [77], that conservatively account for gender, age, discounting, relapse, and unaided cessation. Third, to examine whether iCanQuit costs less than QuitGuide to add greater quality to each life year added [93], a separate ICER quality of life analysis called incremental cost-per-QALY will be conducted ($\text{Total Cost}_{\text{iCanQuit}} - \text{Total Cost}_{\text{QuitGuide}} / (\text{QALY}_{\text{iCanQuit}} - \text{QALY}_{\text{QuitGuide}})$). This analysis will be calculated by adding a Generalized Linear Model-based weighted quality of life parameter derived from the standard EQ-5D quality of life measure [99] taken at the 12-month endpoint. Finally, we will conduct multi-way sensitivity analyses of these results using 1000 Markov Chain Monte Carlo simulations that will derive a cost-effectiveness plane (and 95% CI ellipse) across a range of total costs and effect sizes. In all estimates, we will adjust future costs to a standard reference year and discount future costs and benefits incurred after one year at 3% per annum as is recommended by the USPSTF on cost-effectiveness in health and medicine [100].

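### Aim 3 gives full life-year credit on an endpoint that by implication covers cigarettes only, with no planned check for continued use of other combusted tobacco

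*Combined protocol and SAP*

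**What the plan says.** The Aim 1 paragraph under Primary assessments sets the "Primary endpoint: 30-day point prevalence abstinence at 12-months post randomization" and does not name the products it covers. Further on it adds: "The secondary definition of cessation will include abstinence from cigarettes" and also "non-cigarette nicotine/tobacco products: e-cigarettes, snus, chewing and smokeless tobacco, hookahs, cigars, cigarillos, tobacco" pipes and kreteks. It says that nicotine and tobacco use is recorded at baseline and at every follow-up.

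The Aim 1 analysis section lists, as one of several additional analyses, "using a secondary cessation outcome of no use of cigarettes" and of other nicotine or tobacco products, with approved nicotine replacement allowed. The Aim 3 analysis section does not mention this outcome.

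Under Aim 3, the cost-per-quitter ratio divides by the between-arm difference in participants who are 30-day abstinent at 12 months. For the life-year ratio: "Life years added attributable to each intervention's 12-month primary endpoint effect size will be derived from the life years estimates" in a cited source, "that conservatively account for gender, age, discounting, relapse, and unaided cessation". The QALY ratio adds a quality-of-life weight to this. The planned sensitivity analysis runs 1000 simulations over ranges of total cost and effect size.

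Eligibility admits users of other products on one condition: "if concurrently using any other tobacco products (e.g., e-cigarettes), wants to quit using them within the next 30 days".

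**The concern.** If the primary endpoint already covered other products, a secondary definition that adds them would change nothing. The natural reading is that the primary endpoint counts cigarettes only. Aim 3 turns that endpoint into life-years, and the listed adjustments do not include other tobacco use. A participant who has given up cigarettes but still smokes cigars, cigarillos, a pipe, a hookah or kreteks at 12 months is therefore credited like someone who has stopped smoking altogether.

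The Aims section says Aim 3 is meant to inform payers and policymakers who must decide whether to adopt iCanQuit. The benefit side of each ratio is a small difference between two small counts, so modest misclassification can move it noticeably. A difference in switching between arms would also distort the comparison itself.

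**Working it through.** **The plan's own figure.** The documents give no life-year or cost-effectiveness result to reproduce. The only related computable figure is the sample size: 11% versus 7%, two-sided 0.05, 80% power, stated as 1622 in total. The usual pooled formula is n per arm = [1.96·√(2·0.09·0.91) + 0.84·√(0.11·0.89 + 0.07·0.93)]² / 0.04². It gives 803 per arm, or 1606 in total, and power at 811 per arm is 80.4%. The stated figure reproduces closely. The point below uses the projected rates but does not depend on that calculation.

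**Inputs from the documents.** Projected 12-month quit rates are 11% for iCanQuit and 7% for QuitGuide (Power), with 1250 per arm (opening summary). The Power section counts missing participants as smokers, so the rates apply to everyone randomized.

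- iCanQuit: 1250 × 0.11 = 137.5 abstinent
- QuitGuide: 1250 × 0.07 = 87.5 abstinent
- Difference: 50

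**Inputs that are assumptions.** Let s₁ (iCanQuit) and s₂ (QuitGuide) be the shares of cigarette-abstinent participants still using other combusted tobacco. The documents give neither. Let c be the fraction of a full quitter's life-year gain that such a person deserves: c = 0 is the extreme case, c = 0.5 is half credit.

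**Formula.** Corrected difference = 137.5·[1 − s₁(1 − c)] − 87.5·[1 − s₂(1 − c)]. Factor = 50 / corrected difference. A factor above 1 means the planned life-year difference is too large. With equal shares and c = 0 the factor reduces to 1/(1 − s).

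| s₁ | s₂ | Corrected difference, c = 0 | Factor, c = 0 | Factor, c = 0.5 |
|---|---|---|---|---|
| 2% | 2% | 49 | 1.02 | 1.01 |
| 5% | 5% | 47.5 | 1.05 | 1.03 |
| 10% | 10% | 45 | 1.11 | 1.05 |
| 20% | 20% | 40 | 1.25 | 1.11 |
| 30% | 30% | 35 | 1.43 | 1.18 |
| 10% | 5% | 40.6 | 1.23 | 1.10 |
| 20% | 10% | 31.25 | 1.60 | 1.23 |
| 10% | 15.7% | 50 | 1.00 | 1.00 |
| 5% | 10% | 51.9 | 0.96 | 0.98 |
| 10% | 20% | 53.75 | 0.93 | 0.96 |

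**Break-even.** There is no bias when 137.5·s₁ = 87.5·s₂, that is, when s₂/s₁ = 11/7 = 1.57, whatever the value of c. Above that ratio the planned difference is too small rather than too large.

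**The case against.** A reader might infer something stronger: that life-years gained are overstated and cost per life-year understated, full stop. The documents do not support that, for four reasons.

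- The reported quantity is a between-arm difference. Its bias can vanish or reverse, and neither arm's share is known.
- Cost per life-year is understated only if iCanQuit costs more and the life-year difference is overstated. Aim 3 explicitly asks whether iCanQuit costs less, and no cost figures are given. With a zero or negative cost difference the factors above do not describe an understated cost.
- Zero credit is an extreme. Someone who has given up at least five cigarettes a day and occasionally uses a hookah may well have gained something. Half credit cuts 1.60 to 1.23.
- The cited life-year tables may rest on cigarette quitters who include some users of other products. In that case the planned endpoint would match them and a stricter definition would create a mismatch. This cannot be checked from the documents.

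Two further arguments say the matter is small or already covered. Eligibility requires a wish to quit other products, which may keep the share low. But that is an intention: the same wish is required for cigarettes, and the plan still projects only 11% and 7% abstinent. It also does not prevent later uptake of another product.

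The planned simulations vary effect size. Sampling error alone gives a 95% interval of 50 ± 1.96 × 1250 × √[(0.11·0.89 + 0.07·0.93)/1250], or about 22 to 78 extra quitters, and every corrected difference in the table lies inside it. A wide range around a misclassified centre does not move the centre, however, and does not tell a payer which value goes with which definition of quitting.

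What stands: direction and size are open, and replacing the base case would be hard to justify. What the objections do not remove is the missing check.

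**Conclusion.** The point holds in conditional form. By implication of the outcome and Aim 1 analysis sections, Aim 3 rests on cigarette abstinence alone. It gives continuing users of other combusted tobacco full quitter credit, and no named analysis would show the effect. The incremental life-years, and with them the ratios, may be biased.

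With equal shares of 5% to 20% and no credit, the life-year difference is overstated by a factor of 1.05 to 1.25, and by less with partial credit. With unequal shares the scenarios tried run from 1.60 down to 0.93. All of this rests on assumed shares, on the projected 11% and 7%, and on life-year tables that could not be inspected. That the primary endpoint covers only cigarettes is an inference, though a clear one.

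This is a cheap improvement to Aim 3. It does not touch the primary efficacy analysis.

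**What to change.** 1. State in the endpoint definition that the primary outcome covers cigarettes only.
2. Keep that outcome as the Aim 3 base case, so that Aim 3 stays consistent with Aim 1.
3. Pre-specify two Aim 3 sensitivity analyses that recompute the cost-per-quitter, life-year and QALY ratios: (a) with the all-product definition already planned for Aim 1; (b) counting as quitters only those abstinent from cigarettes and from the other combusted products in the protocol's list. Version (b) is needed because (a) also reclassifies e-cigarette, snus and smokeless users. It is possible only if the six tobacco-use items separate the products; the survey table does not show their wording, so this should be confirmed.
4. Report, by arm, the share of cigarette-abstinent participants still using other combusted tobacco at 12 months. This settles the direction of any bias.

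The cost is a few lines of analysis plan and re-runs on data the plan already schedules, subject to the item check in step 3. The downside is a little more analysis and possibly a less favourable, less precise ratio under the stricter definitions.

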Aim 3. Determine whether iCanQuit is significantly more cost-effective than QuitGuide, as measured by cost per additional quitter, incremental cost-effectiveness ratio (ICER), and incremental cost per quality-adjusted life year (QALY). Importance of

this aim: will provide payers (e.g., insurance companies) and policymakers results needed to decide whether to adopt iCanQuit.

[figure not shown]
Exploratory Aim: Explore whether iCanQuit, as compared to QuitGuide, has higher quit rates for those with these baseline factors: (a) low acceptance of sensations, emotions, and thoughts that cue smoking, (b) heavy smoking (≥ 20 cigarettes/day), (c) current mental health symptoms, and (d) being racial/ethnic minority. Importance of this aim: will potentially identify key subgroups that benefit most from iCanQuit, and thereby aid in reducing tobacco-related health disparities.

Innovations. (1) ACT's innovative features augment the US Clinical Practice Guidelines; (2) ACT follows an innovative theory: Relational Frame Theory; (3) ACT on the smartphone is novel; (4) First randomized trial of a smartphone app for adult smoking cessation; (5) The first time that the following have been tested for **any** behavior outcome: (a) ACT delivered via smartphone, (b) mediation of the effects of a smartphone app, (c) cost-effectiveness of a smartphone app, and (d) exploration of subgroups who benefit most from a smartphone app. While there are thousands of apps and hundreds for smoking [2], testing an app's efficacy is scientifically innovative. That's a critical gap this application fills.

Approach

Randomized trial experimental design. We will conduct a fully-powered two-arm randomized controlled trial that compares iCanQuit to QuitGuide, which follows the USCPG. To balance baseline variables between the two conditions, we will stratify randomization by daily smoking frequency (≤ 20 vs. ≥ 21), education (\leq high school vs. \geq some college), race/ethnicity (minority race/ethnicity vs. non-Hispanic White) and depression screen (CES-D score ≤ 15 vs. ≥ 16). Moderators will be measured at baseline. Mediators will be measured at baseline and three months post randomization. Consistent with cessation trial designs [60], cessation and cost-effectiveness outcomes will be measured at 3, 6, and 12 months post randomization.

Figure 1. Experimental Design

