Aim 2: ACT Mediators. Acceptance of internal cues to smoke: Measured using the Avoidance and Inflexibility Scale (AIS; $\alpha = .93$; [16, 20], which assesses one's willingness to experience sensations (9 items), emotions (9 items), and thoughts (9 items) that cue smoking. A sample item for the sensations scale is: "To what degree did you allow yourself to have urges to smoke?" Commitment to quitting. Commitment to quitting despite internal (e.g., cravings, anxiety) and external (e.g., smoking in the social environment) cues to smoke will be measured using the Commitment to Quitting Scale (CQS; $\alpha = .93$; [59]). Sample item: "No matter how many people around me smoke, I won't let myself smoke once I quit." Regarding assessment timing, three months post randomization is when we expect acceptance and commitment to increase the most, as consistent with past ACT smoking cessation studies [16, 17, 20, 82], and would allow testing of our hypothesized model of increases in acceptance and commitment at three months mediating the impact of the intervention on smoking cessation by twelve months.

Aim 3: Costs of delivery, for cost-effectiveness analyses. Costs associated with each app's delivery include the cost to: (1) host the servers and databases, (2) conduct software updates to accommodate ongoing changes in operating systems, (3) have programming staff to answer technical questions, and (4) cost of facilities and equipment needed to maintain each (e.g., office space for personnel, computers). NCI, the host of QuitGuide, has agreed to provide these costs for QuitGuide [32]. Research-related costs will not be included.

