Exploratory aim: Moderators of treatment outcome. Hypothesized moderators of treatment effectiveness will be heaviness of smoking (smoking at least 20 cigarettes per day vs. less than 20 at baseline), acceptance of cravings to smoke (AIS scores below vs. above the median), mental health symptoms (positive vs. negative screen for depression, anxiety, or heavy alcohol use), and racial/ethnic minority status (Caucasian vs. minority). Mental health symptoms will be assessed as follows: (1) depression screening via the 10-item Center for Epidemiologic Studies Depression Scale (CES-D; cutoff ≥ 10) [83, 84]; (2) anxiety screening via the Generalized Anxiety Disorder Scale; (GAD-7; cutoff ≥ 10 , [85]); (3) alcohol screening via the Alcohol Use Disorders Identification Test—Consumption items (AUDIT-C; cutoffs ≥ 4 drinks/day for women, ≥ 5 drinks/day for men or 7 drinks/week for women, 14 drinks/week for men [86, 87]).

Treatment acceptability/adherence: Treatment satisfaction and utilization. Measured with the 8-item Treatment Satisfaction/Utilization Scale used in our pilot. Sample satisfaction item: "Overall, how satisfied are you with your assigned app?" Sample utilization items: "Overall, about how many times per week did you use the strategies taught in your assigned app?" and "How useful was your assigned app's quit plan?"

Cessation pharmacotherapy usage: Measures number of days per week, number of total weeks, and start/end dates, that participants on their own elected to use (1) nicotine replacement therapy (i.e., patch, gum, lozenge, inhaler, nasal spray), (2)

varenicline, (3) bupropion, and (4) other (fill in).

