(ACT intervention), the mediator M (change from baseline to 3-months post randomization in the acceptance variable, and/or commitment to quitting smoking despite internal cues), and the binary endpoint Y at 12-months post-randomization (e.g., 30-day abstinence). The first regression describes the total intervention effect (X) on the outcome (Y): $\text{logit}(Y) = \gamma_1 + \tau X$, where the parameter τ measures the total intervention effect. The second regression describes the impact of the intervention (X) on the mediator (M): $M = \gamma_2 + \alpha X$. The third regression describes the simultaneous impacts of the intervention (X) and mediator (M) on the outcome (Y): $\text{logit}(Y) = \gamma_3 + \tau'X + \beta M$. Since the endpoint is binary, the mediation effect is the product term $\alpha\beta$, whose empirical distribution will be estimated via 5000 bootstrapped samples. Bootstrapping is a resampling method which provides a powerful test of mediation that does not rely on normality assumptions [93-95]. Randomization should remove potential confounding effects [92, 93], and if needed, we will adjust each model by covariates that differ at baseline or predict outcome. Following VanderWeele and Preacher methods [94, 95], we will also explore any interactions between mediators and treatment arm. And we will explore whether utilization of assigned app and usage of cessation pharmacotherapy mediates cessation outcomes.

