Participants who quit smoking may experience some discomfort associated nicotine withdrawal. Participants will also be fully informed of the symptoms of nicotine withdrawal during the informed consent process. Interventions in all treatment arms provide strategies designed to cope more effectively with symptoms of nicotine withdrawal. Finally, participants in both treatment groups will be given information on pharmacotherapy for smoking cessation (e.g., nicotine patch) and how to obtain these medications.

Reporting breaches and complaints

Taken together, these measures will minimize risks to study participants. However, should a breach/complaint occur, or if a participant is not pleased with any of the surveys, or with the study's procedures, the study's scientific staff will attempt to address the concerns; if unsuccessful, the breach/complaint will be reported to the IRB office, and the participant will be referred to the Fred Hutch IRO Director.

Potential benefits of the proposed research to the subjects and others

Successfully assisting people who smoke to quit would have significant positive benefits to their health. Overall, participants assigned to any of the three interventions have the potential to benefit by quitting smoking and the potential short and long term health benefits of quitting.

Importance of knowledge to be gained

As millions of people are choosing smartphone apps to help them quit smoking, this innovative study shows exciting promise for improving the success rates of quit smoking apps and thereby lowering healthcare costs and reducing premature tobacco-related deaths.

Inclusion of women and minorities

The population for this study will be 2500 adult male and female daily smokers who want to quit smoking. Recruitment and eligibility screening methods are designed to achieve a broad representation of adult smokers, including 70% female and 30% racial/ethnic minority.

Inclusion of children

This is a study of adult smoking cessation; participants will be aged 18 or older. The NIH definition of children includes young adults up to age 21. By the NIH definition, the only “child” participants in this study will be those aged 18-21, over the age of majority and fully capable of participating in informed consent. Therefore, no special protections are required for their inclusion in this research.

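### Aim 3 counts only app-delivery cost; if cessation-medication use differs by arm, all three cost-effectiveness ratios omit part of the incremental cost

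*Combined protocol and SAP*

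**What the plan says.** The Specific Aims say that Aim 3 "will provide payers (e.g., insurance companies) and policymakers results needed to decide whether to adopt iCanQuit".

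On the cost side, the assessment section on Aim 3 begins "Costs associated with each app's delivery include the cost to: (1) host the servers and databases" and adds three more items: software updates, programming staff for technical questions, and the facilities and equipment behind each app. One exclusion is stated: "Research-related costs will not be included". The analysis section for Aim 3 defines cost per quitter as the "difference in total cost of delivering the two interventions [98] divided by the difference in the number of 30-day abstinent participants at 12-months". The ratios per life year and per QALY put the same total-cost difference in the numerator. A set of 1000 simulations varies total cost and effect size; medication is not named there.

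On medication, the section on cessation pharmacotherapy usage says that the survey "Measures number of days per week, number of total weeks, and start/end dates, that participants on their own elected to use" nicotine replacement, varenicline, bupropion or another product. Table 4 schedules the extra-aids items at 3, 6 and 12 months and assigns them to Aim 1 and exploratory work, not to Aim 3. The section on withdrawal discomfort says that "participants in both treatment groups will be given information on pharmacotherapy for smoking cessation (e.g., nicotine patch) and how to obtain these medications". The Aim 2 analysis will explore whether "usage of cessation pharmacotherapy mediates cessation outcomes". Even the stricter cessation outcome under Aim 1 lets users of approved nicotine replacement count as abstinent.

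No section prices medication, names a costing perspective or explains why medication is left out.

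**The concern.** The two sides of each ratio differ in scope. The numerator holds what it costs to run the apps. The denominator, directly or through life years and QALYs, reflects all quits, including those reached with medication that someone paid for.

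This matters only through the difference between arms. If one app leads more of its users to medication, or to dearer medication, part of that arm's extra quits comes with a cost that the ratio does not show. A payer reading the result as the cost of an additional quitter would see an incremental cost that is too low if iCanQuit users take more medication, and too high if QuitGuide users do.

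**Working it through.** **1. The plan's own figure.** Aim 3 states no figure, so the check starts from the quit rates it depends on. The Power section gives 11% versus 7%, two-sided alpha 0.05, 80% power and a total of 1622 (811 per arm).

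n per arm = [1.96 × √(2 × 0.09 × 0.91) + 0.842 × √(0.11 × 0.89 + 0.07 × 0.93)]² / 0.04² = 803 after rounding up, so 1606 in total. This is within 1% of 1622. Power at 811 per arm is 80.4% by formula and 80.6% by simulation. The stated figure reproduces.

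**2. The denominator.** The planned size is 1250 per arm, and the Power section counts missing participants as smokers, so the rates apply to everyone randomised.

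- iCanQuit: 1250 × 0.11 = 137.5 abstinent
- QuitGuide: 1250 × 0.07 = 87.5 abstinent
- Difference: 50 additional quitters

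**3. The omitted cost.** Let d be the difference between arms in the share using medication and c the cost per user, taken as equal in both arms for simplicity.

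Shift per additional quitter = (1250 × d × c) / 50 = 25 × d × c

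Neither d nor c is in the documents. The values below are assumptions.

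| Difference in use | 100 dollars per user | 400 dollars per user |
|---|---|---|
| 0 points | 0 | 0 |
| 1 point | 25 × 0.01 × 100 = 25 | 25 × 0.01 × 400 = 100 |
| 5 points | 25 × 0.05 × 100 = 125 | 25 × 0.05 × 400 = 500 |

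Entries are dollars per additional quitter, and the sign follows the arm with more use. At trial level the largest entry is 1250 × 0.05 × 400 = 25,000 dollars. That same amount would be missing from the numerators of the other two ratios. Their denominators are not projected in the documents, so no shift per life year or per QALY can be given.

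**4. Does the plan allow for a difference?** In the Aim 2 model the mediator equation is M = γ2 + αX, and the mediated effect is αβ. If medication use is taken as M, a non-zero αβ needs a non-zero α, that is, a difference in medication use between arms. So the case the plan sets out to explore under Aim 2 is the case in which Aim 3 omits an incremental cost.

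**5. Do the planned simulations cover it?** They vary total cost, but the Aim 3 analysis defines total cost as delivery cost. Nothing in them carries an arm difference in medication.

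**The case against.** The strongest reply is that the ratios are incremental, so medication cost common to both arms drops out, and that the design points towards similar use. People already using other cessation treatment are ineligible, both arms receive the same kind of medication information, use is by the participant's own choice, and neither app is described as supplying medication. Exploring a mediator is not predicting one. The delivery-cost scope is also open to view, and it would be defensible if it were declared as the perspective. All of this stands. It makes the error conditional; it does not rule it out.

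A reader might infer more than the documents support:

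- *That quits reached through medication are credited to the app free of charge.* This holds only for a difference between arms.
- *That medication would outweigh the delivery-cost difference or reverse its sign.* No delivery cost is given for either app, so the comparison cannot be made.
- *That pricing the medication would yield a payer perspective.* The listed medication items do not include who paid, or the dose, and other health-care use is not counted.
- *That the plan departs from the costing guidance it cites.* Those sources are not part of the documents, so this cannot be claimed.

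One counter-argument does not hold. The word *include* could suggest an open list of costs, but the Aim 3 analysis section confines the numerator to delivery.

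**Conclusion.** The concern holds in conditional form. Aim 3 is addressed to payers, counts delivery cost only, and would omit an incremental cost if medication use or cost per user differs by arm. With equal use and equal cost per user the error is zero.

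Its size and direction cannot be fixed from the documents. The range of 0 to 500 dollars per additional quitter rests on the planned 11% versus 7%, an assumed difference in use of 0 to 5 points, and an assumed 100 to 400 dollars per user. Nothing shows that an adoption decision would change. The primary endpoint and its analysis are unaffected. A change is still worthwhile, because the use data are already being collected and the planned simulations do not address the gap.

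**What to change.** In the Aim 3 cost-assessment and analysis sections:

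1. Label the three planned ratios as delivery-cost perspective and keep them as they are.
2. Pre-specify one sensitivity set of the same three ratios. Each participant's cost is delivery cost plus recorded medication use (product, days per week, weeks) multiplied by a unit price, whoever paid. Fix the price list before arm-level results are seen. Label the set *delivery plus cessation medication*, not payer perspective.
3. Handle missing medication use by multiple imputation, as already planned for missing outcomes. Expected retention is 84%, so about 16% will lack these data.
4. Carry the arm difference in medication cost into the planned simulations.

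The work is a price list, imputation of medication use and one further run of the cost analysis; no new use data are needed. The downside is that self-reported use, with no dose or payer listed, makes the costing approximate. Intervals will be wider, and non-response may bias the arm difference.
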